6.2 Subject Exclusion Criteria

The subject must be excluded from participating in the trial if the subject:

1. Is currently participating and receiving study therapy or has participated in a study of an investigational agent and received study therapy, or used an investigational device within 4 weeks of the first dose of treatment.
2. Has a diagnosis of immunodeficiency or is receiving systemic steroid therapy or any other form of immunosuppressive therapy within 7 days prior to the first dose of trial treatment.
3. Has a known history of active TB (Bacillus Tuberculosis)
4. Hypersensitivity to pembrolizumab or any of its excipients.
5. Has had a prior anti-cancer monoclonal antibody (mAb) within 4 weeks prior to study Day 1 or who has not recovered (i.e., \leq Grade 1 or at baseline) from adverse events due to agents administered more than 4 weeks earlier.
6. Has had prior chemotherapy, targeted small molecule therapy, or radiation therapy within 2 weeks prior to study Day 1 or who has not recovered (i.e., \leq Grade 1 or at baseline) from adverse events due to a previously administered agent.
 - Note: Subjects with \leq Grade 2 neuropathy are an exception to this criterion and may qualify for the study.
 - Note: If subject received major surgery, they must have recovered adequately from the toxicity and/or complications from the intervention prior to starting therapy.
7. Has a known additional malignancy that is progressing or requires active treatment. Exceptions include basal cell carcinoma of the skin or squamous cell carcinoma of the skin that has undergone potentially curative therapy or in situ cervical cancer.

8. Has known active central nervous system (CNS) metastases and/or carcinomatous meningitis. Subjects with previously treated brain metastases may participate provided they are stable (without evidence of progression by imaging for at least four weeks prior to the first dose of trial treatment and any neurologic symptoms have returned to baseline), have no evidence of new or enlarging brain metastases, and are not using steroids for at least 7 days prior to trial treatment. This exception does not include carcinomatous meningitis which is excluded regardless of clinical stability.
9. Has active autoimmune disease that has required systemic treatment in the past 2 years (i.e. with use of disease modifying agents, corticosteroids or immunosuppressive drugs). Replacement therapy (e.g., thyroxine, insulin, or physiologic corticosteroid replacement therapy for adrenal or pituitary insufficiency, etc.) is not considered a form of systemic treatment.
10. Has immunohistochemically proven mismatch repair deficient cancer (this test is standard in our center for colorectal and endometrial cancer patients, and documentation will be required to be negative to accept outside referrals with colorectal or endometrial cancer for this trial).
11. Has a history of (non-infectious) pneumonitis that required steroids or current pneumonitis
12. Evidence of interstitial lung disease.
13. Has an active infection requiring systemic therapy.
14. Has a history or current evidence of any condition, therapy, or laboratory abnormality that might confound the results of the trial, interfere with the subject's participation for the full duration of the trial, or is not in the best interest of the subject to participate, in the opinion of the treating investigator.
15. Has known psychiatric or substance abuse disorders that would interfere with cooperation with the requirements of the trial.
16. Is pregnant or breastfeeding, or expecting to conceive or father children within the projected duration of the trial, starting with the pre-screening or screening visit through 120 days after the last dose of trial treatment.
17. Has received prior therapy with an anti-PD-1, anti-PD-L1, or anti-PD-L2 agent.
18. Has a known history of Human Immunodeficiency Virus (HIV) (HIV 1/2 antibodies).
19. Has known active Hepatitis B (e.g., HBsAg reactive) or Hepatitis C (e.g., HCV RNA [qualitative] is detected).
20. Has received a live vaccine within 30 days of planned start of study therapy.

Note: Seasonal influenza vaccines for injection are generally inactivated flu vaccines and are allowed; however intranasal influenza vaccines (e.g., Flu-Mist®) are live attenuated vaccines, and are not allowed.

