5.3. Rationale for Endpoints

5.3.1 Efficacy Endpoints

The primary efficacy endpoint is overall Immune-Related Objective Response Rate (IR-ORR).

Secondary efficacy endpoints will include Progression Free Survival (PFS) and Overall Survival (OS).

We expect that pembrolizumab will have a higher clinically meaningful antitumor activity, as measured by IR-ORR and PFS in patients with solid tumors with functional deficiency in the Fanconi Anemia (FA) pathway, compared to those with functionally competent repair.

Based on our prior screening data, we anticipate that close to 30% of patients with solid tumors, depending on tumor type will be FA functionally deficient and that the response rate in these patients will be very similar than what was seen for patients with mismatch repair deficient colorectal cancer. The latter will not be included in this trial as we are trying to identifying another subset of highly responsive patients.

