Albumin	$\geq 2.5 \text{ mg/dL}$
Coagulation	
International Normalized Ratio (INR) or Prothrombin Time (PT)	$\leq 1.5 \times$ ULN unless subject is receiving anticoagulant therapy as long as PT or PTT is within therapeutic range of intended use of anticoagulants
Activated Partial Thromboplastin Time (aPTT)	$\leq 1.5 \times$ ULN unless subject is receiving anticoagulant therapy as long as PT or PTT is within therapeutic range of intended use of anticoagulants

^aCreatinine clearance should be calculated per institutional standard.

8. Female subject of childbearing potential should have a negative urine or serum pregnancy within 72 hours prior to receiving the first dose of study medication. If the urine test is positive or cannot be confirmed as negative, a serum pregnancy test will be required.
9. Female subjects of childbearing potential (Section 5.7.2) must be willing to use an adequate method of contraception as outlined in Section 5.7.2 – Contraception, for the course of the study through 120 days after the last dose of study medication.
10. Male subjects of childbearing potential (Section 5.7.1) must agree to use an adequate method of contraception as outlined in Section 5.7.1- Contraception, starting with the first dose of study therapy through 120 days after the last dose of study therapy.

Note: For 9 and 10, abstinence is acceptable if this is the usual lifestyle and preferred contraception for the subject.

6.1.1 Expansion Cohort.

Ten (10) additional subjects with the diagnosis of metastatic or recurrent endometrial carcinoma will be enrolled in the trial at the conclusion of regular enrollment with subject with the eligibility discussed in 6.1., and as per Sample size Calculation and Statistics Section (Section 12). The following will be necessary criteria for this expansion cohort.

1. Diagnosis of Endometrial Carcinoma or Sarcoma which is metastatic and has failed standard treatment or is recurrent, or for which standard chemotherapy is contraindicated or refused by patient.
2. Sufficient tissue is available for correlative studies as specified on Section 9.0.2.8.
3. MSI studies have been performed, either by immunohistochemistry or next generation sequencing and results show that patient is MS low or stable.
4. Patient meet all the inclusion criteria discussed above on 6.1 and none of the exclusion criteria discussed below on section 6.2.

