7.2 Subject Replacement Strategy

We anticipate enrollment of 39 patients for which tumor and toxicity assessments following pembrolizumab administration can be made. We will replace patients enrolled for which clinical trial discontinuation was performed prior to any administration of pembrolizumab or those for which pembrolizumab is discontinued due to acute hypersensitivity reactions during the first administration of pembrolizumab. An attempt will be made to assess tumor response in all enrolled patients as specified in the protocol. However, patients experiencing clinical deterioration after two doses of pembrolizumab, will be considered treatment failures and will count as tumor progression. These patients will not be replaced.

We are also expecting that 30% of the patients enrolled will be negative on the FATS1 assay, which will be conducted in batched analyses.

See section 6.1.1 and 12.0.1 for expansion cohort.

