12.0 SAMPLE CALCULATION AND STATISTICAL ANALYSIS PLAN

The primary endpoint is overall immune-related objective response rate. We expect that similar to mismatch repair deficient patients, the immune-related objective response will be at or above 40% in patients with functional FA deficiency (FATSI negative), and less than 10% in patients without either homologous recombination repair deficiency or mismatch repair deficiency. Patients with mismatch repair deficiency will be excluded from this trial. Based on our prior screening data, we anticipate that close to 30% of patients with solid tumors, depending on tumor type will be FA functionally deficient.

We will utilize a two-stage phase II trial design to detect an iORR of at least 20% in the whole population tested vs. the null hypothesis that the true iORR is at most 5%, representing a response by chance alone, or other infrequent unknown mechanism. Specifically, we will test the null hypothesis $H_0: \text{iORR} \leq 5\%$ vs. $H_1: \text{iORR} \geq 20\%$ with 90% power and a Type I error rate of 10%. The alternative hypothesis of 20% iORR represents a weighted average of the anticipated 40% response in FATSI-negative patients and 10% response in FATSI-positive, assuming a 3 to 7 ratio of these patient groups. Interim analysis requires that at least two of the first 20 evaluable patients enrolled have an objective response. If this occurs, we will accrue 19 additional patients for a total of 39. Overall rejection criterion of the null hypothesis is observing at least 4 responses.

The proposed two-stage design was chosen instead of the Simon Optimal or Minimax design because it has a larger first stage enrollment and thus a higher expected number of FATSI-negative patients in the interim analysis. Total enrollment of 39 patients is only slightly greater than that of the Simon designs but has the advantage of increasing the expected number of FATSI-negative patients. Additionally, the proposed design has a higher early stopping probability under the null hypothesis. The following table summarizes these operating characteristics.

Table 10:

Design	First stage enrollment	Expected		Total enrollment	Total expected FATSI-patients	Actual α	Power	Expected study size
		FATSI-patients, 1 st stage	PET					
Optimal	12	4	0.54	37	11	0.093	90.2%	23
Minimax	18	5	0.40	32	10	0.072	90.1%	26
Proposed	20	6	0.74	39	12	0.099	91.7%	25

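### Section 12.0 says mismatch-repair-deficient patients are excluded, but exclusion 10 removes only proven cases; separately, the rule for counting treated patients without a scan is incomplete.

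*Combined protocol and SAP*

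**What the plan says.** **Mismatch repair.** Section 12.0 states: "Patients with mismatch repair deficiency will be excluded from this trial". The operative rule is Section 6.2, exclusion 10. It applies to a patient who "Has immunohistochemically proven mismatch repair deficient cancer (this test is standard in our center for colorectal and endometrial cancer patients" and adds, for patients from elsewhere, that "documentation will be required to be negative to accept outside referrals with colorectal or endometrial cancer for this trial". Exclusion 14 (conditions that might confound the results) rests on the investigator's opinion and asks for no test. Section 5.3.1 states a narrower intention, about mismatch-repair-deficient colorectal cancer: "The latter will not be included in this trial as we are trying to identifying another subset of highly responsive patients". The endometrial expansion cohort, which lies outside the main 39, has its own requirement in Section 6.1.1: "MSI studies have been performed, either by immunohistochemistry or next generation sequencing and results show that patient is MS low or stable".

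**Decision rule.** Section 12.0 tests a response rate of at most 5% against at least 20% in the whole population tested. It describes the 5% as "representing a response by chance alone, or other infrequent unknown mechanism". "Interim analysis requires that at least two of the first 20 evaluable patients enrolled have an objective response"; the null is rejected with at least 4 responses in 39.

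**Counting.** Section 7.2 describes the 39 as patients in whom tumour and toxicity assessments can be made. It replaces patients never dosed and "those for which pembrolizumab is discontinued due to acute hypersensitivity reactions during the first administration of pembrolizumab". Clinical deterioration after two doses counts as progression, without replacement. For the rest it promises an attempt at assessment. The term evaluable is not defined.

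**Approved indications.** Section 2.0 admits only patients without an approved or compendia-listed indication. Section 6.1, inclusion item 6, lets uninsured or denied patients be considered case by case.

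**The concern.** The trial looks for a responsive group other than mismatch-repair deficiency, and Section 12.0 reads as though deficiency had been removed from the population. For tumours other than colorectal and endometrial, nothing in the eligibility rules ensures that. Section 4.4 reports high response rates in deficient tumours, colorectal or not. With so low a bar, one response from a patient whom the plan believes excluded could turn a negative trial positive or move the FATSI contrast. A reader of the report would credit that response to the wrong mechanism.

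The counting gap is separate. A treated patient who withdraws, dies, stops for other toxicity or deteriorates after one dose, all before the first scan, falls under no stated rule. If the choice is made once responses are known, the denominator can be chosen to suit the result.

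**Working it through.** **Inputs.** From Section 12.0: 5% null, 20% alternative, at least 2 of 20 to continue, at least 4 of 39 to reject, stated type I error 0.099 and power 91.7%. From Section 4.4: response in deficient tumours of 4/10 (40%, colorectal) and 5/7 (71%, non-colorectal). Not in the documents, hence assumed: the number of undetected deficient patients and the share of treated patients without an assessment.

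1. **The plan's own figures.** P(positive) = Σ over x ≥ 2 of P(X₁ = x; n = 20) × P(X₂ ≥ 4 − x; n = 19). At 5% this is 0.0993 and at 20% it is 0.9165. Both match Table 10.

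2. **One undetected deficient patient.** Place that patient at random among the 39, with response probability q, and let the other 38 respond at 5%. P(positive) is 0.2309 if that patient responds and 0.0924 if not.
   - q = 40%: 0.40 × 0.2309 + 0.60 × 0.0924 = 0.148.
   - q = 71%: 0.71 × 0.2309 + 0.29 × 0.0924 = 0.191.
   - Share of positives that depend on that response, q × (0.2309 − 0.0924) / P(positive): 0.40 × 0.1385 / 0.148 = 37%; 0.71 × 0.1385 / 0.191 = 52%.
   - Mean true rate, (38 × 5% + q) / 39: 5.9% and 6.7%. A uniform rate at those values gives 0.153 and 0.208.

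3. **The 5% null read as already including that patient.** The others then respond at (39 × 5% − q) / 38 = 4.08% or 3.26%, and P(positive) is 0.093 or 0.076.

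4. **Benchmark.** With every patient at 5% and none deficient, 62% of positive results have exactly 4 responses, so losing any one responder reverses them.

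5. **Leaving out one deficient responder.** The overall estimate moves from 4/39 (exact 90% interval 3.6% to 22.0%) to 3/38 (2.2% to 19.2%). Table 11's limits reproduce as Wald limits: difference − 1.645 × √[p₁(1 − p₁)/n₁ + p₂(1 − p₂)/n₂]. For 4/12 vs 2/27 this is +2.1%. It becomes −3.7% if the patient left out was FATSI-negative (3/11 vs 2/27) and +6.3% if FATSI-positive (4/12 vs 1/26).

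6. **Size of the untested group, for illustration.** In Table 1, 643 − 167 colon − 14 rectal − 13 endometrial = 449 (70%), or about 27 of 39 on that mix. The enrolled mix may differ. At an assumed prevalence π of 1%, 2% or 5%, the chance of at least one case, 1 − (1 − π)²⁷, is 24%, 42% or 75%. The width of that range shows that the documents cannot settle the matter.

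7. **Denominator.** Suppose a share d of treated patients, all non-responders, is dropped and the all-treated rate is 5%. The rate among those counted is 0.05/(1 − d). For 1 of 40 it is 5.13% and type I error is 0.106; for d = 5% it is 5.26% and 0.114. If instead two of the 39 are kept as non-responders and the rest respond at 5%, it is 0.086.

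8. **Power with all treated patients counted.** If the 20% target is per assessable patient, the rate is 0.20 × (1 − d). For 1 of 40 (19.5%) power is 0.907; for 5% (19%) 0.897; for 10% (18%) 0.872. If the target is per treated patient, power stays 0.917.

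**The case against.** The strongest reply is that no error rate is wrong. Section 12.0 tests the whole population treated, so an undetected deficient patient belongs to it. A reader might take 0.148 to 0.191 as an inflated type I error; that does not follow. These are rejection probabilities when the true rate is about 5.9% to 6.7%, above the null, and step 3 shows no inflation if the null already covers such patients. This part of the reply stands.

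It also stands that any responder can be pivotal when the bar is 4 (step 4), that the 40% and 71% come from 10 and 7 patients, and that Sections 5.3.2 and 12.0 already call the FATSI results exploratory and underpowered. The expansion cohort's MSI requirement is weak evidence of a double standard, since exclusion 10 already covers endometrial cancer. The intention in Section 5.3.1, read narrowly as colorectal, is met.

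On counting, a reader might infer that Section 7.2 has no rule for patients lost before the first scan. It has two: first-infusion hypersensitivity and deterioration after two doses can both precede it. Nor does it permit dropping other patients, so 0.106 and 0.114 describe what silence allows and not what is planned.

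The reply does not remove the mismatch between Section 12.0 and exclusion 10, nor the undefined term evaluable.

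**Conclusion.** The point holds in a limited form. Section 12.0 claims a property of the population that exclusion 10 does not deliver for tumours other than colorectal and endometrial. The type I error of 0.099 is correct as stated; it is the interpretation of a positive result that is exposed. If exactly one undetected deficient patient entered and the rest responded at 5%, 37% to 52% of positive results would rest on that patient's response. The documents do not support saying that such a patient is likely, because they give no prevalence.

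The counting rule is incomplete, not absent. Its effect is modest: 0.114 on an all-treated basis under an assumed 5% of treated patients dropped, all non-responders, and below 0.099 if such patients stay in the 39 as non-responders.

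The difference between Sections 2.0 and 6.1 on approved indications is a matter of wording. Overall these are changes the sponsor should make; none of them invalidates the design.

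**What to change.** 1. **Section 12.0, mismatch repair.** Reword the exclusion statement to match exclusion 10: proven cases are excluded, with testing described for colorectal and endometrial cancer.
2. **Sensitivity analysis.** Keep the primary set intact. Prespecify a repeat of the response rate and of the FATSI comparison that leaves out tumours found mismatch-repair deficient or MSI-high in the planned tumour sequencing, where the assay can make that call. Fix the threshold beforehand, apply it blind to response, and report unclassifiable tumours separately. Sections 5.3.2 and 12.2 already plan tumour sequencing and mutation load, but do not show that the assay can call MSI, so the unclassifiable group may be large.
3. **Counting.** Define evaluable. For both 2/20 and 4/39, count any treated patient without a post-baseline tumour assessment as a non-responder, and do not replace that patient in the efficacy count. Also report an all-treated response rate that includes patients replaced for first-infusion hypersensitivity.
4. **Power.** State in Section 12.0 whether the 20% target is per treated patient (0.917) or per assessable patient (0.907 with 1 of 40 unassessed, 0.897 at 5%, 0.872 at 10%). The last two fall below the planned 90%.
5. **Approved indications.** Reconcile the wording of Section 2.0 with inclusion item 6 of Section 6.1.

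The sample size, decision thresholds and eligibility tests do not change. The cost is wording, one additional analysis, and a slightly lower response rate if some treated patients are never assessed.

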6.3 Trial Treatments

The treatment to be used in this trial is outlined below in Table 3.

Table 3. Trial Treatment

Drug	Dose/Potency	Dose Frequency	Route of Administration	Regimen/Treatment Period	Use
Pembrolizumab	200 mg	Q3W	IV infusion	Day 1 of each 3 week cycle	Experimental

Trial treatment should begin on the day of randomization or as close as possible to the date on which treatment is allocated/assigned.

6.4 Dose Selection/Modification

Dose Selection

The rationale for selection of doses to be used in this trial is provided in Section 4.0 – Background and Rationale. Details on preparation and administration of pembrolizumab (MK-3475) are provided in the Package Insert.

Dose Modification (Escalation/Titration/Other)

Adverse events (both non-serious and serious) associated with pembrolizumab exposure may represent an immunologic etiology. These adverse events may occur shortly after the first dose or several months after the last dose of treatment. Pembrolizumab must be withheld for drug-related toxicities and severe or life-threatening AEs as per Table 4 below. See Section 6.8.1 for supportive care guidelines, including use of corticosteroids.

Table 4. Dose Modification and Toxicity Management Guidelines for Immune-related AEs Associated with Pembrolizumab

General instructions:

1. Corticosteroid taper should be initiated upon AE improving to Grade 1 or less and continue to taper over at least 4 weeks.
2. For situations where pembrolizumab has been withheld, pembrolizumab can be resumed after AE has been reduced to Grade 1 or 0 and corticosteroid has been tapered. Pembrolizumab should be permanently discontinued if AE does not resolve within 12 weeks of last dose or corticosteroids cannot be reduced to ≤ 10 mg prednisone or equivalent per day within 12 weeks.
3. For severe and life-threatening irAEs, IV corticosteroid should be initiated first followed by oral steroid. Other immunosuppressive treatment should be initiated if irAEs cannot be controlled by corticosteroids.

Immune-related AEs	Toxicity grade or conditions (CTCAEv4.0)	Action taken to pembrolizumab	irAE management with corticosteroid and/or other therapies	Monitor and follow-up
Pneumonitis	Grade 2	Withhold	
 Administer corticosteroids (initial dose of 1-2 mg/kg prednisone or equivalent) followed by taper 	
 Monitor participants for signs and symptoms of pneumonitis Evaluate participants with suspected pneumonitis with radiographic imaging and initiate corticosteroid treatment Add prophylactic antibiotics for opportunistic infections
	Grade 3 or 4, or recurrent Grade 2	Permanently discontinue		
Diarrhea / Colitis	Grade 2 or 3	Withhold	
 Administer corticosteroids (initial dose of 1-2 mg/kg prednisone or equivalent) followed by taper 	
 Monitor participants for signs and symptoms of enterocolitis (ie, diarrhea, abdominal pain, blood or mucus in stool with or without fever) and of bowel perforation (ie, peritoneal signs and ileus). Participants with \geq Grade 2 diarrhea suspecting colitis should consider GI consultation and performing endoscopy to rule out colitis. Participants with diarrhea/colitis should be advised to drink liberal quantities of clear fluids. If sufficient oral fluid intake is not feasible, fluid and electrolytes should be substituted via IV infusion.
	Grade 4	Permanently discontinue		
AST / ALT elevation or Increased bilirubin	Grade 2	Withhold	
 Administer corticosteroids (initial dose of 0.5-1 mg/kg prednisone or equivalent) followed by taper 	
 Monitor with liver function tests (consider weekly or more frequently until liver enzyme value returned to baseline or is stable)
	Grade 3 or 4	Permanently discontinue	
 Administer corticosteroids (initial dose of 1-2 mg/kg prednisone or equivalent) followed by taper 	

Type 1 diabetes mellitus (T1DM) or Hyperglycemia	Newly onset T1DM or Grade 3 or 4 hyperglycemia associated with evidence of β -cell failure	Withhold	
 Initiate insulin replacement therapy for participants with T1DM Administer anti-hyperglycemic in participants with hyperglycemia 	
 Monitor participants for hyperglycemia or other signs and symptoms of diabetes.
Hypophysitis	Grade 2	Withhold	
 Administer corticosteroids and initiate hormonal replacements as clinically indicated. 	
 Monitor for signs and symptoms of hypophysitis (including hypopituitarism and adrenal insufficiency)
	Grade 3 or 4	Withhold or permanently discontinue ¹		
Hyperthyroidism	Grade 2	Continue	
 Treat with non-selective beta-blockers (eg, propranolol) or thionamides as appropriate 	
 Monitor for signs and symptoms of thyroid disorders.
	Grade 3 or 4	Withhold or permanently discontinue ¹		
Hypothyroidism	Grade 2-4	Continue	
 Initiate thyroid replacement hormones (eg, levothyroxine or liothyroinine) per standard of care 	
 Monitor for signs and symptoms of thyroid disorders.
Nephritis and Renal dysfunction	Grade 2	Withhold	
 Administer corticosteroids (prednisone 1-2 mg/kg or equivalent) followed by taper. 	
 Monitor changes of renal function
	Grade 3 or 4	Permanently discontinue		
Myocarditis	Grade 1 or 2	Withhold	
 Based on severity of AE administer corticosteroids 	
 Ensure adequate evaluation to confirm etiology and/or exclude other causes
	Grade 3 or 4	Permanently discontinue		
All other immune-related AEs	Intolerable/persistent Grade 2	Withhold	
 Based on type and severity of AE administer corticosteroids 	
 Ensure adequate evaluation to confirm etiology and/or exclude other causes
	Grade 3	Withhold or discontinue based on the type of event. Events that require discontinuation include and not limited to: Gullain-Barre Syndrome, encephalitis		

	Grade 4 or recurrent Grade 3	Permanently discontinue		

1. Withhold or permanently discontinue pembrolizumab is at the discretion of the investigator or treating physician.
 
NOTE: For participants with Grade 3 or 4 immune-related endocrinopathy where withhold of pembrolizumab is required, pembrolizumab may be resumed when AE resolves to \leq Grade 2 and is controlled with hormonal replacement therapy or achieved metabolic control (in case of T1DM).
				

Dosing interruptions are permitted in the case of medical / surgical events or logistical reasons not related to study therapy (e.g., elective surgery, unrelated medical events, patient vacation, and/or holidays). Subjects should be placed back on study therapy within 3 weeks of the scheduled interruption, unless otherwise discussed with the Sponsor. The reason for interruption should be documented in the patient's study record.

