10.0.1.0 Safety Follow-Up Visit

The mandatory Safety Follow-Up Visit should be conducted approximately 30 days after the last dose of trial treatment or before the initiation of a new anti-cancer treatment, whichever comes first. All AEs that occur prior to the Safety Follow-Up Visit should be recorded. Subjects with an AE of Grade > 1 will be followed until the resolution of the AE to Grade 0-1 or until the beginning of a new anti-neoplastic therapy, whichever occurs first. SAEs that occur within 90 days of the end of treatment or before initiation of a new anti-cancer treatment should also be followed and recorded.

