	Dechallenge	
Was Merck product discontinued or dose/exposure/frequency reduced?
 
If yes, did the AE resolve or improve?
 
If yes, this is a positive dechallenge. If no, this is a negative dechallenge.
 
(Note: This criterion is not applicable if: (1) the AE resulted in death or permanent disability; (2) the AE resolved/improved despite continuation of the Sponsor's product; or (3) the trial is a single-dose drug trial); or (4) Sponsor's product(s) is/are only used one time.)
	
	Rechallenge	
Was the subject re-exposed to Merck product in this study?
 
If yes, did the AE recur or worsen?
 
If yes, this is a positive rechallenge. If no, this is a negative rechallenge.
 
(Note: This criterion is not applicable if: (1) the initial AE resulted in death or permanent disability, or (2) the trial is a single-dose drug trial); or (3) Sponsor's product(s) is/are used only one time).
 
NOTE: IF A RECHALLENGE IS PLANNED FOR AN ADVERSE EVENT WHICH WAS SERIOUS AND WHICH MAY HAVE BEEN CAUSED BY MERCK PRODUCT, OR IF REEXPOSURE TO MERCK PRODUCT POSES ADDITIONAL POTENTIAL SIGNIFICANT RISK TO THE SUBJECT, THEN THE RECHALLENGE MUST BE APPROVED IN ADVANCE BY THE SPONSOR AS PER DOSE MODIFICATION GUIDELINES IN THE PROTOCOL.
	
	Consistency with Trial Treatment Profile	Is the clinical/pathological presentation of the AE consistent with previous knowledge regarding Merck product or drug class pharmacology or toxicology?	
The assessment of relationship will be reported on the case report forms /worksheets by an investigator who is a qualified physician according to his/her best clinical judgment, including consideration of the above elements.			
Record one of the following		Use the following scale of criteria as guidance (not all criteria must be present to be indicative of Merck product relationship).	
Yes, there is a reasonable possibility of Merck product relationship.		There is evidence of exposure to Merck product. The temporal sequence of the AE onset relative to the administration of Merck product is reasonable. The AE is more likely explained by Merck product than by another cause.	

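### Table 4 withholds pembrolizumab for Grade 1 myocarditis, yet its general restart rule allows re-dosing when a Grade 2 myocarditis has fallen only to Grade 1

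*Combined protocol and SAP*

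**What the plan says.** Section 6.4 makes the Table 4 holds mandatory: "Pembrolizumab must be withheld for drug-related toxicities and severe or life-threatening AEs as per Table 4 below". The myocarditis row reads "Myocarditis Grade 1 or 2 Withhold", with permanent discontinuation at Grade 3 or 4. Its management columns call for corticosteroids according to severity and a work-up of the cause. They give no restart grade.

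Restart is governed by general instruction 2 at the head of the table, which covers all situations where the drug has been withheld: "pembrolizumab can be resumed after AE has been reduced to Grade 1 or 0 and corticosteroid has been tapered". The same instruction adds a 12-week limit: "Pembrolizumab should be permanently discontinued if AE does not resolve within 12 weeks of last dose". Instruction 1 requires any steroid taper to begin once the event is at Grade 1 or less and to last at least 4 weeks.

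The only event-specific exception to the restart rule is the NOTE under Table 4, which begins "For participants with Grade 3 or 4 immune-related endocrinopathy where withhold of pembrolizumab is required" and does not reach myocarditis.

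**The concern.** Most rows of Table 4 start withholding at Grade 2 or above, so a general restart threshold of Grade 1 or 0 sits below the hold threshold and the two rules fit together. Myocarditis was given a stricter hold threshold, Grade 1, but no matching restart threshold. For a Grade 2 myocarditis that improves to Grade 1 and stays there, the row says hold and instruction 2 says the drug may be given. Two investigators could treat the same patient differently and both could claim to follow the protocol.

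What is at stake is re-exposure to the drug during ongoing immune-related cardiac toxicity. Neither the flow chart (Section 8.1) nor the laboratory table (Section 9.0.2.9) schedules a cardiac test such as an ECG or troponin that would inform the decision to restart.

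**Working it through.** The plan states no figure on this point, so the main check is a comparison of rules.

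**1. Hold grades against restart grades**

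| Table 4 rows | Hold triggered at | Overlap with restart range {0, 1} |
|---|---|---|
| Pneumonitis, diarrhea/colitis, AST/ALT or bilirubin, hypophysitis, hyperthyroidism, nephritis, all other irAEs (7 rows) | Grade 2 or higher | None |
| T1DM/hyperglycemia (1 row) | New onset, or Grade 3-4 with beta-cell failure | Restart addressed by the NOTE |
| Myocarditis (1 row) | Grade 1 or 2 | Grade 1 |
| Hypothyroidism (1 row) | No hold (continue) | Not applicable |

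Ten rows, nine with a withhold action; one of the nine overlaps the general restart range, at Grade 1 only.

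**2. Which patients are affected.** Instruction 2 speaks of an event that has been reduced to Grade 1 or 0. A myocarditis that begins at Grade 1 has not been reduced to Grade 1, so it is outside the problem. Grade 3-4 events are permanently discontinued. What remains is Grade 2 falling to a persistent Grade 1.

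**3. When restart becomes possible.** If steroids were given, at least 4 weeks after Grade 1 is reached (instruction 1). If none were given, at the next scheduled dose, at most 3 weeks later plus the 3-day window.

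**4. Whether another provision requires Grade 0**

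- *The 12-week limit.* It turns on whether the event resolves and names no grade. Section 10.0.1.0 shows how the protocol uses that word: "Subjects with an AE of Grade > 1 will be followed until the resolution of the AE to Grade 0-1". On that usage a persistent Grade 1 counts as resolved. Reading it as Grade 0 would also sit badly with the preceding sentence of instruction 2, which allows restart at Grade 1.
- *The rechallenge note in Section 11.0.4.* For a serious, possibly drug-caused event, or where re-exposure adds significant risk, "THEN THE RECHALLENGE MUST BE APPROVED IN ADVANCE BY THE SPONSOR AS PER DOSE MODIFICATION GUIDELINES IN THE PROTOCOL". It sets no grade and refers back to the same dose modification rules.
- *The NOTE under Table 4.* Endocrinopathies only.
- *Section 6.8.1.* No myocarditis entry.
- *Section 7.0.* Discontinuation for unacceptable adverse experiences or on the investigator's decision; no restart grade.

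None requires Grade 0.

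**5. Rough frequency.** The documents give no incidence, so p, the proportion of patients with Grade 1-2 myocarditis, is an assumption. With n = 39 + 10 = 49 (main cohort in Section 12.0 plus expansion cohort in Section 12.1), expected cases = 49p and P(at least one) = 1 − (1 − p)^49.

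| Assumed p | Expected cases | P(at least one) |
|---|---|---|
| 0.1% | 0.05 | 4.8% |
| 0.5% | 0.25 | 21.8% |
| 1% | 0.49 | 38.9% |

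These figures are for any Grade 1-2 myocarditis. The affected subset is smaller by an amount the documents do not allow one to estimate.

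**The case against.** The best counter-argument is that both rules can be obeyed at once. Instruction 2 is a permission and the row is a mandatory hold. If the specific limits the general, a patient still at Grade 1 stays held, and the row itself supplies the Grade 0 requirement. It is true that continued withholding breaches nothing. But the protocol states no order of precedence, and instruction 2 is written for exactly the situation in which the drug has already been withheld. If the stricter reading is intended, it needs to be written down.

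Second, overlap alone need not be an error. Hypophysitis is held at Grade 2, yet the NOTE lets a held Grade 3-4 endocrinopathy restart at Grade 2 or lower. That is correct, but the allowance is express and depends on hormonal or metabolic control. It shows an event-specific exception being written where one is meant, and myocarditis has none.

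Third, sponsor approval under the rechallenge note, the investigator's power to withdraw a patient, and the steroid and work-up instructions are real safeguards. They make a careless restart less likely. None tells the decision-maker which grade is acceptable.

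Fourth, Grade 0 can be called a clinical preference, since Section 11.0.4 describes Grade 1 generally as mild. For this event, however, the plan has already decided that Grade 1 warrants a hold, and Grade 0 follows from that threshold.

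The rarity stands in full.

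**Conclusion.** The inconsistency is real and narrow. As written, Section 6.4 permits re-dosing of a Grade 2 myocarditis that has settled at Grade 1, the grade at which its own row withholds the drug, and nothing elsewhere requires Grade 0. The conclusion rests on the text alone: on instruction 2 applying to every hold, and on there being no stated rule that the row prevails. The frequency range depends on the assumed incidence and is an upper bound for the affected patients under that assumption.

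This is a minor safety correction that should be made. It has no bearing on the sample size, the interim stopping rule, or the type I error and power.

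**What to change.** Add one line to the myocarditis row of Table 4, marked as an exception to general instruction 2:

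*Resume only after resolution to Grade 0 and completion of any corticosteroid taper. If Grade 0 is not reached within 12 weeks of the last dose, permanently discontinue.*

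Grade 0 has to be named in the 12-week clause as well, because Section 10.0.1.0 treats Grade 0-1 as resolution.

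The change needs an amendment of one line and adds no procedures, visits or patients. Its clinical cost is that a rare patient with persistent Grade 1 myocarditis, possibly one whose tumor is responding, would be unable to restart.
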